Study Design:	
Phase 1 prospective non-randomised safety cohort study with all patients recruited from a single UK site (Oxford). The study has an open label design with all participants receiving ThermoDox® and FUS. The study will run in two parts. Part I is required to identify optimal FUS exposure parameters using real time thermometry data from an implanted thermometry device, such as a thermistor. Part II does not require implantation of thermometry device and is designed to more accurately reflect how the therapy would be implemented in clinical practice. All evaluable participants from both Part I and Part II will be included in the endpoint analysis.
 
Part I
 
For each participant, a single liver tumour will receive the intervention and follow-up imaging. The ability to achieve targeted release of doxorubicin from ThermoDox® at the tumour site will be determined using three tumour biopsies with corresponding peripheral blood samples taken during intervention and/or using a radiological method (MR-Spectroscopy).
 
Part II
 
For each participant, a single liver tumour will receive the intervention and follow-up imaging.. The optimal FUS exposure parameters determined in Part I will be selected for Part II interventions, accounting for differences in propagation path length identified in the Ultrasound Session. The ability to achieve targeted release of doxorubicin from ThermoDox® at the tumour site will be determined using the same methods as for Part I, with the exception of requiring only two tumour biopsies.
 
In the 30 days following intervention, both Part I and II participants will be followed up with a maximum of two CTs, two PET-CTs and three MRI/MR-Spectroscopy scans. There is however built in flexibility for the scans to be performed at different timepoints up to 60 days post intervention should the patient provide this optional consent and not have started another treatment. If available, other non-FUS control tumour(s) in the liver exposed to ThermoDox® alone will be selected as controls against which radiological response in the FUS-targeted tumour (target tumour) will be compared.
 
Detailed criteria for evaluation of efficacy and safety are described in subsequent sections.

Patient Numbers:	A maximum of 28 evaluable participants will be recruited to the study overall.
Target Population:	Adult patients with incurable (unresectable, non-ablatable-for-cure) confirmed hepatic primary (hepatocellular carcinoma or cholangiocarcinoma) or secondary (metastatic) tumour. All patients will have progressed or maintained stability on conventional chemotherapy. To be suitable, patients must have liver tumour(s) in the liver of size 1cm or greater, which are amenable to ultrasound-guided biopsy.
Objectives:	
PRIMARY OBJECTIVE:
 
To determine whether targeted release of doxorubicin from ThermoDox® ('drug') using mild hyperthermia generated non-invasively by focused ultrasound (FUS) is feasible in cancer patients.
 
SECONDARY OBJECTIVES:
 
 Part I only: To determine optimal FUS exposure parameters for a range of participant Body Mass Indices (BMIs) and tumour locations within the liver

	
 To assess the safety of FUS-induced mild hyperthermia for drug delivery To assess the local and systemic cytotoxic effects of ThermoDox® in this setting 
TERTIARY (EXPLORATORY) OBJECTIVES: Regarding those participants for which doxorubicin has been released by optimal FUS exposure parameters:
 
 To establish the validity of other minimally-invasive and non-invasive methods of evaluating intratumoural uptake of doxorubicin as an alternative to that used in primary endpoint: 
 a) Fluorescence microscopy of biopsy b) MR-Spectroscopy c) Plasma pharmacokinetics To determine whether the dose of doxorubicin released has a therapeutically significant effect on the target tumour.
Rationale:	
The development of distant spread (metastases) is a leading cause of death in patients with advanced solid tumours. The liver is one of the most common sites for metastatic disease. Studies have shown that the treatment of distant metastases improves survival. Life expectancy for patients with metastatic colorectal cancers without treatment ranges from 5 to 9 months with a median survival after diagnosis of 6 months [1-3]. Surgical resection remains the only treatment shown to have long-term curative potential [4]. However, only a minority (10-20%) of patients are surgical candidates [5]. Systemic chemotherapy is the current treatment of choice for patients with inoperable liver metastasis. However, long-term survival is rare. The majority of primary liver cancers (hepatocellular carcinoma (HCC) and cholangiocarcinoma) are unresectable and survival remains dismal [6-9]. Post-hoc analysis of the Phase III HEAT study is indicative that ThermoDox® treatment improves survival in patients with HCC, where Radiofrequency Ablation (RFA) was optimal.
 
This proof of concept study proposes targeted delivery of broad-spectrum cytotoxic agent (doxorubicin), via a specially formulated LTSL (ThermoDox®) activated by mild hyperthermia, as both a feasible and effective solution to the drug-delivery problem for the same systemic dose. Recent animal work performed at Oxford using ThermoDox® released using FUS has shown that increased uptake at the target site is achievable. It is proposed that this method of targeted drug delivery is clinically applicable, and may achieve increased tumour uptake and local dose for the equivalent dose of doxorubicin used in systemic chemotherapy, which has a well-established and safe toxicity profile.
 
Clinical studies have demonstrated:
 
 The safety profile of ThermoDox® has been shown to be consistent with that of doxorubicin (HEAT study) ThermoDox® treatment shows promise for improved progression-free survival and overall survival in the subset HCC of patients having optimal RFA (HEAT study) ThermoDox® has demonstrated a dose-response effect against metastatic liver tumours [10] 
If this study demonstrates successful targeted drug delivery in human subjects using ThermoDox® combined with mild-hyperthermia, this could potentially transform the future of chemotherapy in clinical practice; targeted therapy using LTSLs containing other chemotherapeutic agents triggered non-invasively by mild hyperthermia could be applied to any solid tumour.

Primary Endpoint:	A demonstrable two-fold increase in, or value exceeding 10µg/g of, the concentration of intra-tumoural doxorubicin at the treated tumour site following FUS-induced mild hyperthermia, in at least 50% of evaluable participants.
Secondary Endpoints:	
 Part I only: Achievement of the desired range of mild hyperthermia in the target tissue as monitored by the implanted thermometry device during FUS exposure

	
 2. Persistence of cell viability stain or percentage of cell or tissue necrosis under 30% following FUS exposure, as assessed by cytological or histological methods 3. Significant bone marrow suppression, deranged liver function and liver toxicity. 4. Adverse events up to 30 days post-intervention: 
 a. Deemed related to ThermoDox® b. Deemed related to FUS
Tertiary (Exploratory) Endpoints:	
Regarding doxorubicin released by optimal FUS exposure parameters:
 
 1. Combined analysis of relevant end points to establish most effective alternative analytical method(s) for quantifying drug release: 
 a. Released biopsy samples exhibiting averaged regions of nuclear or background fluorescence levels at least twice that of a suitable control, as assessed by fluorescence microscopy b. Liver MRI/MR-Spectroscopy indicating targeted delivery of doxorubicin to the tumour by demonstrating a statistically significant increase in the tumour:background ratio of signal intensity following intervention compared to baseline c. A significant decrease of in total doxorubicin plasma levels over time-matched clearance levels, following FUS-induced release 2. Radiological evidence of tumour response at timepoints up to 60 days post-intervention in the FUS-targeted tumour and control(s), as assessed by Principles of Choi and RECIST response evaluation using MRI and CT [11, 12] and SUV_{max} using PET-CT [13]
Inclusion Criteria	
Patients will only be eligible for inclusion in this study if all of the following criteria apply:
 
 1. Pathologically confirmed advanced solid tumour with liver metastasis suitable for intervention (as assessed by ultrasound or other radiological methods). In addition confirmed primary liver tumours (hepatocellular carcinoma or cholangiocarcinoma) can be included. 2. Will have progressed or remained stable on conventional chemotherapy. 3. Male or Female, Age ≥ 18 years. 4. Have life expectancy of ≥ 3 months. 5. Left Ventricular Ejection Fraction (LVEF) ≥ 50% on echocardiogram. 6. Have not received radiotherapy to the target area within the preceding 12 months. 7. A World Health Organisation (WHO) performance status of ≤ 1 (Appendix 1). 8. Able and willing to give written informed consent, indicating that they are aware of the investigational nature of this study and potential risks, and able to comply with the protocol for the duration of the study, including scheduled follow-up visits and examinations.
Exclusion criteria	
Patients will be ineligible for recruitment to the study if any of the following conditions hold:
 
 1. Have surgery or other procedure requiring general anaesthesia planned to be undertaken during the period of the study. 2. Have serious illnesses including, but not limited to, congestive heart failure (NYHA class III or IV functional classification); life threatening cardiac arrhythmia; or myocardial infarction or cerebral vascular accident within the last 6 months. 3. Have on going significant infection (chest, urine, blood, intra-abdominal). 4. Have uncontrolled diabetes. 5. Have received a life-time dose of doxorubicin > 450mg/m² or a life-time dose of epirubicin > 900mg/m² or any dose of both. 6. Pregnant or breast-feeding. In women of childbearing potential, a negative

	
pregnancy test (serum) is required within 30 days prior to study intervention.
 
 7. Female participants of child bearing potential and male participants whose partner is of child bearing potential who are not willing to practice an acceptable form of contraception (i.e. oral contraceptive, diaphragm, cervical cap, condom, surgical sterility) during the study and for 6 months thereafter. Women whose partner has or men who have undergone a vasectomy must use a second form of birth control. 8. Have any known allergic reactions to any of the drugs or liposomal components or intravenous imaging agents to be used in this study. 9. Have portal or hepatic vein tumour invasion/thrombosis. 10. Inadequate haematological and biochemical function (section 4.1.2) 11. Have contraindications to receiving doxorubicin including prior sensitivity (rash, dyspnoea, wheezing, urticarial or other symptoms) attributed to anthracyclines or other liposomal drugs. 12. Use of chemotherapy or of an investigational drug within 30 days or 5 half-lives, whichever is longer, preceding the intervention. 13. Have medically significant active infection. 14. Have Child-Pugh Class C liver disease, or Class A-B with encephalopathy and/or refractory ascites (Appendix 3). 15. Documented HIV positive. 16. Documented diagnosis of haemochromatosis. 17. Documented history of contrast-induced nephropathy. 18. Have any of the following contraindications for liver biopsy: 
 a. Suspected liver haemangioma or other vascular tumour b. Tense ascites c. Known cystic liver disease* d. Extra-hepatic biliary obstruction* 
(* Relative contraindications only and may be non-exclusive at discretion of the study team)
 19. Other medical or psychiatric conditions or laboratory abnormalities that the investigator considers would make the patient a poor trial candidate.
Trial dose and administration:	
The investigative medicinal product is ThermoDox® LTSL doxorubicin. It is supplied in 20cc vials each vial containing 30mg doxorubicin in 15ml of solution. A carton containing 4 vials is normally sufficient for one treatment of one subject.
 
One single dose of ThermoDox® with a doxorubicin concentration of 50mg/m² will be given during the FUS exposure session as an intravenous infusion for both Part I & II.

Duration on study:	30 days from intervention (Day 1) with a maximum of 60 days of radiological follow-up
Study Procedures and frequency:	
Part I
 
Part I is concerned with optimisation of the FUS acoustic parameters. The optimal FUS exposure parameters to achieve the desired range of mild hyperthermia in the target tumour (and consequent ThermoDox® release) will be determined. A single target liver tumour will have already been identified. The participant requires insertion of a co-axial needle during intervention for monitoring and biopsy; consequently Part I is minimally invasive.
 
Day -1: Attend for oral premedication and for baseline radiological assessment (Liver MRI/MR-Spectroscopy, Liver pCT and whole body FDG PET-CT scans)
 
Day 1: Target tumour exposed to a combination of FUS and ThermoDox® under General Anaesthetic. Three liver tumour biopsies and temperature readings are taken via a single co-axial needle. Three peripheral blood samples are taken for

		
plasma pharmacokinetics.
 
Day 2: Peripheral blood samples (FBC, U&E, LFT) are taken. Repeat Liver MRI/MR-Spectroscopy is performed within 36 hours of intervention. Participant is discharged after a minimum of 24 hours of observation post-intervention.
 
Follow-up: Clinical reviews and repeat set of blood samples (FBC, U&E, LFT) at Days 15 and 30. A maximum of two further sets of scans (Liver MRI/MR-Spectroscopy, Liver pCT and whole body FDG PET-CT) are performed within 60 days post-intervention (one at 4 week follow-up, the other being flexible).
 
Part II
 
Part II is concerned with monitoring efficacy of the intervention (ThermoDox® release by mild hyperthermia), using the optimised FUS acoustic parameters identified in Part I. In particular, the release of doxorubicin and its therapeutic effect will be investigated. A single liver tumour will have been identified for intervention.. The participant requires insertion of a co-axial needle during intervention for a biopsy of the tumour area receiving FUS exposure for HPLC and microscopy analysis, and consequently Part II is minimally invasive.
 
Day -1: As for Part I.
 
Day 1: Target tumour exposed to a combination of FUS and ThermoDox® under General Anaesthetic. Two biopsies of the tumour receiving intervention are taken via a single co-axial needle. Peripheral blood samples are taken for plasma pharmacokinetics.
 
Day 2: As for Part I.
 
Follow-up: As for Part I.

Patient care post-trial:		Patients will be managed as per standard of care.
Criteria for evaluation	Safety:	Safety and toxicity will be reported using NCI CTCAE (currently version 4.03).
	Efficacy:	Efficacy will be assessed by evidencing targeted ThermoDox® release, as per the primary endpoint. In addition radiological response will be assessed as a tertiary endpoint.
Pharmacokinetic assays:		Analysis of plasma samples to capture plasma pharmacokinetics of doxorubicin.
Histopathology:		Histological analysis of biopsy samples obtained from the targeted liver tumour may be performed by microscopy where tissue mass allows
No. of Study Site(s)		Single Centre UK (OXFORD)
End of study		Last Patient Last Visit
Publication policy		The intention is to publish this research in a specialist peer reviewed scientific journal on completion of the study. The results may also be presented at scientific meetings and/or used for a thesis. The Investigators will be involved in reviewing drafts of the manuscripts, abstracts, press releases and any other publications arising from the trial and retain final editorial control.

SUMMARY OF SCHEDULE EVENTS

Visit Description	Ultrasound Screening ¹		Full Screening & Main Study		Intervention				2wk Follow-up	4wk Follow-up*	Flexible Radiological Follow-up
	Consent	Screening	Consent	Screening							
Visit No.	1a	1b	2a ²	2b ³	3				4	5	Flexible
Visit Type	Outpatient	Outpatient	Outpatient	Outpatient	Outpatient then Inpatient from Day -1 or Day 1 ⁴				Outpatient	Outpatient	Outpatient
Admission Duration (days)	0	0	0	0	3				0	0	0
Day		From -40 to -2		From -30 to -2	(-7 to -1) (Pre-intervention)	-1 (Pre-intervention)	1 (Intervention Day)	2 (Recovery Day)	15	30	12-60**
Visit window (days)		After 1a		After 2a	After 2b				±3	+7 not <30	Not >60
Informed Consent	X		X								
Inclusion / Exclusion Criteria				X							
Demographics, Medical & Surgical History				X							
Concomitant medication				X						X	
Physical Exam & Vital Signs				X				X			
Height				X							
Weight				X		X					
Urinalysis ± Pregnancy Test				X							
ECG				X							
Echocardiogram ⁵				X							

¹ The ultrasound screening may optionally be performed in advance of screening for the main study, or during the study screening.

² Study consent is usually taken during the screening visit but occasionally in advance (e.g. in clinic), but must occur before study procedures are performed outside of standard care.

³ Best efforts will be made to ensure all screening procedures & required tests occur during a single screening visit but, but according to resources and patient preference, one or more additional screening visit(s) may occasionally be required.

⁴ It is not compulsory for participants to be admitted on day -1. I.e. the patient can attend to complete pre-intervention assessments and return on day 1 to be admitted for the intervention.

⁵ Echocardiogram will only be repeated if clinically indicated.

WHO PS				X							
Haematology tests ⁶				X				X	X	X	
Biochemistry tests ⁷				X				X	X	X	
Group & Save ⁸				X							
Coagulation studies ⁹				X							
Pre-operative Anaesthetic Assessment (ASA Classification)				X							
Ultrasound Session ¹⁰		X		X							
Liver MRI/MR Spectroscopy ¹¹					X			X ¹²		X	X
Liver pCT ¹³					X					X	X
Whole Body FDG PET-CT					X					X	X
Pre-medication						X					
FUS + ThermoDox®							X				
ThermoDox® Plasma Samples							X ¹⁴				
Tumour Biopsy Samples							X ¹⁵				
Adverse Event Review							X	X	X	X	

* The 4 week follow-up visit will mark the end of the study and the participant will be free to consider other studies from this point, however scans may be performed after this time point in the flexible scan follow-up visit if that participant is not already enrolled on another study at that time.

** The flexible radiology follow-up visit will be chosen based on patient preference, available imaging slots and emerging radiological data. Patient visits will be minimised where possible. The flexible scan visit will be performed at least a week either side the 4 week follow-up visit, and may coincide with the 2 week follow-up visit.

In Part II, the number of follow-up MRI/MR-Spectroscopy, Liver pCT and whole body FDG PET-CT scans may be reduced, if the data from Part I informs that a more efficient (in terms of reducing patients & site requirements) schedule is possible.

⁶ Full Blood Count (FBC); including Haemoglobin (Hb), white blood cells (WBC) with differential count (neutrophils and lymphocytes) and platelets.

⁷ Biochemical profile to include U&Es, (Na⁺, K⁺, Ur, Cr), phosphate, calcium, LFTs (total protein, ALP, Albumin, ALT or AST, Bili, LDH) (validity period for bloods is 3 days).

⁸ Group & Save, as standard for surgical candidates, date of valid test to be recorded on CRF, not blood group. Can alternatively be performed on d-1.

⁹ Coagulation studies are performed at baseline only (PT & APTT).

¹⁰ During the Ultrasound Session feasibility of intervention is confirmed and a target tumour will be selected by ultrasound. Only one screening ultrasound is required.

¹¹ MRI includes the abdomen. Measurements made using the modified RECIST 1.1 criteria.

¹² Liver MRI includes the abdomen. The first Liver MRI/MR Spectroscopy following intervention can alternatively be performed on the same day as intervention, if intervention is in the morning. It should occur within 36 hours of the completion of intervention, and ideally within 24 hours where possible.

¹³ Liver pCT includes the abdomen. Measurements made using CHOI and the modified RECIST 1.1 criteria.

¹⁴ Three blood samples for pharmacokinetics in both Phases I and II (Pre-Treatment, Unreleased drug, Released drug).

¹⁵ Three biopsies in Part I (Pre-Treatment, Unreleased drug, Released drug), two biopsies in Part II (Released drug).

KEY DEFINITIONS

“Intervention” refers to attempted targeted release of ThermoDox® by mild hyperthermia using a focused ultrasound.

The “FUS-targeted tumour” or “target tumour” refers to the liver tumour treated with FUS following ThermoDox® delivery. This is in contrast to the RECIST definition, which defines target tumours as those measurable lesions which are followed through the patient’s treatment course.

A “non-FUS control tumour” refers to a liver tumour receiving ThermoDox® alone which has been selected for radiological follow-up and comparison with the target tumour.

The “desired range of mild hyperthermia” is used in the context of ThermoDox® release in this study and is defined as achieved bulk tissue temperature in the range of 41-47°C

“Optimal FUS exposure parameters” are defined as those combinations of settings on the HIFU device (power, duty cycle and transducer motion plan) which result in an adequate temperature rise to successfully release doxorubicin from the LTSls in the target tumour, without causing direct thermal tissue damage.

An “evaluable participant” is defined as a participant who has received FUS following delivery of ThermoDox® in Part I or II, and for whom it has been possible to evaluate the outcome of the intervention based on biopsy samples, or radiologically.

An “evaluable sample” is defined as a sample for which sufficient material was available for analysis and the analytical technique has provided quantifiable data.

ABBREVIATIONS

AE	Adverse Event
ADL	Activities of Daily Living
ADR	Adverse Drug Reaction
ALT	Alanine Transaminase
ANC	Absolute Neutrophil Count
ASA	American Society of Anaesthesiologists
AST	Aspartate Transaminase
BD	Bi Daily
BMI	Body Mass Index
CCA	Cholangiocarcinoma
CI	Chief Investigator
CR	Complete Response
CRC	Colorectal cancer
CRF	Case Report Form
CT	Computerized Tomography
CTA	Clinical Trials Authorisation
CTA	Clinical Trial Agreement
CTCAE	Common Toxicity Criteria Adverse Events
CTIMP	Clinical Trial of an Investigational Medicinal Product
DLT	Dose Limiting Toxicity
DNA	Deoxyribonucleic Acid
DSUR	Development Safety Update Report
ECG	Electrocardiogram
eCRF	Electronic Case Report Form
EMA	European Medicines Agency
EP	Early Progression
FBC	Full Blood Count
FDA	Federal Drug Administration
FDG-PET	Fluorodeoxyglucose Positron Emission Tomography
FUS	Focused Ultrasound

GCP	Good Clinical Practice
GI	Gastro-Intestinal
GMP	Good Manufacturing Practices
GP	General Practitioner
Hgb	Haemoglobin
HCC	Hepatocellular Carcinoma
HIFU	High Intensity Focused Ultrasound
HIV	Human Immunodeficiency Virus
IB	Investigators Brochure
ICH	International Conference of Harmonisation
IMP	Investigational Medicinal Product
LDH	Lactate Dehydrogenase
LVEF	Left Ventricular Ejection Fraction
LTLD	Lyso-Thermosensitive Liposomal Doxorubicin
LTSL	Lyso-Thermosensitive Liposome
mCRC	Metastatic Colorectal Cancer
MedDRA	Medical Dictionary for Regulatory Activities
MHRA	Medicines and Healthcare products Regulatory Agency
MRI	Magnetic Resonance Imaging
MTD	Maximum Tolerated Dose
NCI	National Cancer Institute
NE	Not Evaluable
NHS	National Health Service
NIMP	Non-Investigational Medicinal Product
OCTO	Oncology Clinical Trials Office
OCTRU	Oxford Clinical Trials Research Unit
OD	Once Daily
OS	Overall survival
pCT	Perfusion CT
PD	Pharmacodynamic or Progressive Disease
PFS	Progression Free Survival
PI	Principal Investigator
PICs	Participant Identification Centres (PICs)
PIS	Patient Information Sheet
PK	Pharmacokinetic
PO	Per Os (oral)
PR	Partial Response
QT	QT interval
QTc	Corrected QT interval
REC	Research Ethics Committee
RECIST	Response Evaluation Criteria In Solid Tumours
RFA	Radio-frequency Ablation
RR	Response Rate
SAE	Serious Adverse Event
SD	Stable Disease
SOP	Standard Operating Procedure
SUSAR	Suspected Unexpected Serious Adverse Reaction
SUV _{max}	Standardised Uptake Value Maximum [13]
TSC	Trial Steering Committee
TSL	Thermosensitive Liposome
WBC	White Blood Count

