2.2 Duration of patient participation

Participants will be in the study for less than three months following entry on study and the participant will be followed up clinically for a maximum of 37 days and radiologically for a maximum of 60 days after intervention (Day 1).

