2.3 Post-trial care and follow-up

Following the completion of the study, patients will receive standard care until disease progression or death.

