5.3 Follow-up and end of study evaluations (within 60 days)

Follow-up 1: Day 15 (± 3 day tolerance)

Parts I & II:

- Full Blood Count (FBC); including Haemoglobin (Hb), white blood cells (WBC) with differential count (neutrophils and lymphocytes), and platelets
- Biochemical profile; including sodium, potassium, calcium, phosphate, urea, creatinine
- Liver profile; including total protein, albumin, bilirubin, ALP, AST and/or ALT and LDH
- Adverse event monitoring

Follow-up 2: Day 30 (+7 not <30)

Parts I & II:

- Adverse event monitoring
- Concomitant medication recording
- Full Blood Count (FBC); including Haemoglobin (Hb), white blood cells (WBC) with differential count (neutrophils and lymphocytes), and platelets
- Biochemical profile; including sodium, potassium, calcium, phosphate, urea, creatinine
- Liver profile; including total protein, albumin, bilirubin, ALP, AST and/or ALT and LDH

Follow-up Scans: From Day 12 - Day 60 post-intervention as defined in the summary of schedule events (one set of scans at 4 weeks follow-up, the other being flexibly timed in accordance with emerging radiological data from previous study participants)

Parts I & II:

- Maximum of two follow-up Liver MRI/MR-Spectroscopy scans
- Maximum of two follow-up Liver pCT scans
- Maximum of two follow-up whole body FDG PET-CT scans

¹⁸ The time of intervention is defined as the time at which the final FUS exposure is complete

If a participant is withdrawn from the study following the intervention, adverse event recording should continue for 30 days post-intervention. No other follow-up evaluations will be required.

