9.5 Prohibited therapies

Patients should not be prescribed any other anti-cancer or investigational therapies while participating in this study.

9.6 (Potential) Drug Interactions

Investigators should also be aware of potential drug-drug interactions.

Doxorubicin is extensively metabolized by the liver. Changes in hepatic function induced by concomitant therapies may affect doxorubicin metabolism, pharmacokinetics, therapeutic efficacy, and/or toxicity.

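### The synopsis and the schedule note set different conditions for scans after the 4-week visit, so a scan taken after off-study anti-cancer therapy could count towards the exploratory response endpoint

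*Protocol*

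**What the plan says.** **Synopsis, Study Design.** Follow-up scans may be moved to different time points up to 60 days after intervention "should the patient provide this optional consent and not have started another treatment".

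**Summary of Schedule Events, note marked with one asterisk.** "The 4 week follow-up visit will mark the end of the study", and the participant is then free to consider other studies. Scans may still be done later, at the flexible visit, "if that participant is not already enrolled on another study at that time". The note does not mention other treatment.

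**Summary of Schedule Events, note marked with two asterisks.** "The flexible scan visit will be performed at least a week either side the 4 week follow-up visit". It may coincide with the 2-week visit.

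**Section 5.3.** Follow-up scans run "From Day 12 - Day 60 post-intervention as defined in the summary of schedule events". No treatment condition is added.

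**Section 2.3.** "Following the completion of the study, patients will receive standard care until disease progression or death".

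**Section 9.5.** "Patients should not be prescribed any other anti-cancer or investigational therapies while participating in this study".

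**Section 9.4.** Concomitant medication is recorded until the off-study visit. The schedule marks it at screening and at the 4-week visit only.

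**Section 3, Table 3.** The second tertiary objective is assessed by radiological tumour response on scans up to 60 days. It carries the qualifier that the result must be shown in at least half of evaluable participants.

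**The concern.** The two passages apply different tests to the same scan: the synopsis asks whether another treatment has begun, the schedule note whether the participant has joined another study. Standard chemotherapy given outside a study separates them.

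The protocol's own description of the population makes this plausible. Patients have incurable disease, and section 4.1.2 requires at least 30 days without chemotherapy before the intervention. Section 1.1.2 describes systemic chemotherapy as the usual choice for inoperable liver metastases, and section 13.10.1 regards progression as likely in disseminated disease. Some participants may therefore start a new treatment soon after the 4-week visit.

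At stake is the interpretation of the tertiary response endpoint, which asks whether the released doxorubicin has a therapeutic effect on the target tumour. Shrinkage on a scan taken after new systemic therapy would be credited to the study intervention.

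**Working it through.** The plan gives no figure to reproduce. The check compares the conditions and then counts days.

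**1. One participant under both rules.** Suppose the 4-week visit is on Day 30, off-study standard chemotherapy starts on Day 35, and the flexible scan is planned for Day 45.

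| Source | Condition on the scan | Result |
|---|---|---|
| Synopsis | Optional consent given and no other treatment started | Not permitted |
| Schedule note | Not enrolled on another study | Not barred |
| Section 5.3 | Day 12 to Day 60, as the schedule defines | Not barred |

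**2. Does another section close the gap?** Section 9.5 bars other anti-cancer therapy during participation. Whether that lasts beyond the 4-week visit is unclear: the schedule note ends the study there, while section 2.2 continues radiological follow-up to 60 days. Section 2.3 adds only the return to standard care.

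**3. When can a late flexible scan occur?** The 4-week visit is on Day 30 with a window of +7 days, so on Days 30 to 37. The flexible scan must be at least 7 days from it and lie within Days 12 to 60.

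- Visit on Day 30: early scans from Day 12 to 30 - 7 = Day 23; late scans from 30 + 7 = Day 37 to Day 60. That is 12 early and 24 late days, so 24 of 36 permitted days are late.
- Visit on Day 37: early scans from Day 12 to 37 - 7 = Day 30; late scans from 37 + 7 = Day 44 to Day 60. That is 19 early and 17 late days, so 17 of 36 are late.

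The interval between the 4-week visit and the last permitted scan day is 60 - 30 = 30 days or 60 - 37 = 23 days. New treatment could start off-study in that interval before a scan that counts.

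**4. How sensitive is the endpoint?** With the maximum of 28 evaluable participants, 12/28 = 43% and 14/28 = 50%. Two misclassified participants could therefore carry the proportion to the 50% mark. This shows sensitivity only; it does not predict that such cases will occur.

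**5. Would the data reveal the problem?** Taking the off-study visit to be the 4-week visit, required medication recording stops between Day 30 and Day 37. The protocol then does not require the start date of a later treatment to be captured.

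**The case against.** The strongest reply is that the note is silent rather than permissive. It does not say that treated patients may be scanned, nor that study enrolment is the only test. Both conditions can be met together, and the synopsis is current protocol text that a footnote does not cancel. This is fair as to wording: a reader might infer that the schedule positively authorises scans after new treatment, and it does not. What remains is that section 5.3 directs staff to the schedule, where the treatment condition is missing.

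A second reply is that section 9.5 still applies, because section 2.2 and the synopsis entry on duration include radiological follow-up to 60 days. That reading is arguable. It conflicts with the note's end-of-study statement, and it would leave the synopsis condition on other treatment with little to do.

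Third, the consequence is limited. The endpoint is exploratory, section 12 says that the study's success does not depend on follow-up imaging, and a scan set at the 4-week visit is planned regardless. This stands.

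Fourth, a rule for censoring or excluding scans normally belongs in the statistical analysis plan, which was not available here and may contain one. Its absence from the protocol is not criticised. The mismatch between the two protocol passages remains, and so does the early end of medication recording, on which such a rule would depend.

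**Conclusion.** The point holds as an inconsistency within the protocol with a limited consequence. The synopsis and the schedule note must be reconciled. Until they are, a participant on off-study anti-cancer therapy could have a late flexible scan that enters the tertiary response endpoint.

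Three stronger conclusions might be inferred, and the documents support none of them:

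- **A count of affected participants.** Applying an assumed 20-40% to 28 gives 5.6 to 11.2, or about 6 to 11. That requires all 28 places to be filled and every participant to have a late scan. The flexible scan may instead be early, Part II scans may be reduced, and 28 is a maximum. The share starting treatment is not given, so the number may be zero.
- **A share of 30 in 49 days.** Counting Days 31-60 within Days 12-60 ignores the one-week spacing rule. Days 31-36 are never available for a late flexible scan.
- **A spoiled control comparison.** Later systemic therapy would reach the non-FUS control tumour as well, so the within-patient contrast is partly protected. The target tumour's own classification is not, and section 12.2.1 accepts that some participants have no control tumour.

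The primary endpoint rests on biopsies taken on the day of intervention and is unaffected. The conclusion assumes that section 9.5 does not clearly extend past the 4-week visit and that no rule in the unseen analysis plan or case report form already deals with such scans.

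**What to change.** 1. Reconcile the schedule note with the synopsis so that both carry the same condition for scans after the 4-week visit: no other treatment started and not enrolled on another study.
2. Record on the case report form the start date of any new anti-cancer treatment, through the last study scan.
3. Exclude scans after that date from the radiological response endpoint, in the statistical analysis plan if it does not already say so. Such participants are then assessed on their earlier study scans.

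The cost is one clause, one date field and one analysis sentence. The downside is the loss of a few late scans from an exploratory endpoint.
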